4. HR____ BP____ MBP____

SUPPLEMENT 5. Data collection by the patient during the rest of the day**PAIN INTENSITY DURING THE DAY**

This questionnaire is designed to be used by you (participant) 3 to 6 hours after having received the intervention. TIME: _____

Complete the following tables:

1. If you have taken any kind of analgesic drug please fill this table with the following information:

DRUG NAME	TIME	QUANTITY

2. If you have performed any form of non-pharmacological strategy for pain please fill this table with the following information:

USED STRATEGY	TIME	DURATION

Please answer after 3-6 hours have passed from receiving the intervention.

1. With a single mark please answer. How much pain are you feeling right now? Consider 0 as “I’m not feeling any pain” y 10 “I’m feeling the worst pain of my life”. Please mark your answer on the line.

2. Please answer the following questions with: Never, Sometimes, Most of the time o Always.

Question	Never	Sometimes	Most of the time	Always
Have you felt nervous or anxious lately				
Have you felt fearful lately				
Have you been irritated or have you panicked easily				
Have you felt down				
Have you felt tremulous				
Have you felt headache, pain on your back, or pain on your neck				
Have you felt weak and fatigue easily				
Have you felt palpitations or elevated heart rate				
Have you felt dizzy lately				
Have you felt nausea or stomach disturbances lately				

SUPPLEMENT 6. Instructions to receive the intervention

INSTRUCTIONS FOR RECEIVE THE INTERVENTION

Thank you for participating in our study, please read carefully.

WHEN WILL I RECEIVE THE INTERVENTION?

When you **start feeling pain associated to your menses** the intervention will be able to be conducted. At this moment you should contact the researcher¹.

IMPORTANT: If it is not possible to receive the intervention **during the first 12 hours of pain**, the intervention will be avoided and it is recommended give your usual treatment to pain. If this happens, remember that **you are not excluded from the study** you would be able to receive the intervention in the next month.

AT WHAT PLACE WILL THE INTERVENTION TAKE PLACE?

The intervention **will be conducted at the facilities of the Quinta de Mutis** in an assigned place for it. The specific place **will be specified when you contact the** **At what time will the intervention take place?**

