Every package will contain an MP4 electronic device and a set of headphones. Packages will be identical and the music device will be set to look the same visually. The researcher will apply a first questionnaire to collect demographic data, medical history, surgical history, gynecologic and obstetric history, the first VAS evaluating usual pain (VAS1) in dysmenorrhea, and the first measurement of vital signs (all measurements will be collected according the explained protocol in the variables and measurement tool section). After this, another VAS evaluating acute pain (VAS2) and the short version of the Zung's anxiety scale will be collected.

The student will put on the headphones and the researcher will set the volume at 50 dB, and will play the file "AUDIO 1", and then he will leave the place. The volume is under security ranges established by Resolution 8321 of 1983 from the Ministry of Health from Colombia. This established that, the maximum level of sound intensity would be 105 dB for continuous expositions during 1 hour. The student should stay for 30 minutes listening to the AUDIO 1 file following the instructions of the package. The instructions will also explain to the patient that she can't mention what she listened through the headphones (during the intervention or even after it). Additionally, patient will be explained that she can't modify the volume during the 30 minutes. The patient is free to stop the device and the intervention but this should be informed to the investigator immediately. After the 30 minutes of the intervention the researcher will enter again the room.

After ending the intervention and entering back, the researcher will collect the following data: pain perception according to VAS (VAS3), anxiety using the Zung's scale, vital signs, and the patient will be asked if she desires to take any analgesia at that moment. Additionally, the patient will be given another questionnaire that includes: pain perception using a VAS (VAS4), anxiety using the short version of the Zung's scale, information about any drug or other form of analgesia used. This questionnaire should be answered by the student 3-6 hours after the intervention. This questionnaire should be delivered to the investigators. The patients will be able to bring with them any type of analgesic (the ones they usually used) and to initiate their usual analgesia after collection of variables post-intervention.

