Data collection:

The following figure shows the different moments for data collection:

DD, demographic data; MH, medical-surgical history; GH, gyneco-obstetric history; VAS1, usual menses pain; VS, vital signs; VAS2, pain perception before the intervention; ZS1, anxiety before the intervention; VAS3, pain perception after the intervention; ZS2, anxiety after the intervention; AR1, analgesic requirements after the intervention; VAS4, pain perception 6 hours after the intervention; ZS3, anxiety 6 hours after the intervention; AR2, used drugs or other analgesic therapies up to 6 hours after the intervention.

Sample calculation:

Considering the objectives of this study, the main endpoint is the change in pain perception evaluated with a VAS. For the sample calculation a one sided alternative hypothesis, a significance level (*p* value) α of 0.01 and a power (1- β) of 0.90 ($\beta=0.1$) was established.

The following are the null hypothesis (H_0) and alternative hypothesis (H_1):

- H_0 : no differences in the change of the acute pain perception (ΔP) in primary dysmenorrhea, from before the intervention (VAS2) until the moment after the intervention (VAS3), among the control (CG) and the experimental (MG) groups.

$$\begin{aligned} \text{VAS2}_{\text{CG}} - \text{VAS3}_{\text{CG}} &= \text{VAS2}_{\text{MG}} - \text{VAS3}_{\text{MG}} \\ \Delta P_{\text{CG}} &= \Delta P_{\text{MG}} \end{aligned}$$

- H_1 : Students listening to music (MG) will have a larger pain reduction (ΔP), from the moment before the intervention (VAS2) to the moment after (VAS3) the intervention, compared to silence group (CG).

- $VAS2_{CG}-VAS3_{CG} < VAS2_{MG}-VAS3_{MG}$
 - $\Delta P_{CG} < \Delta P_{MG}$

The prevalence of primary dysmenorrhea in the students from two programs (medicine and psychology) of the School of Medicine and Health Sciences from Universida del Rosario was described as 73%, with a mean pain intensity of 5.8 (SD 2.0) using a VAS (27). Nevertheless, no studies reporting the efficacy of music listening for pain relief in dysmenorrhea has been published, therefore there are no data regarding the change of pain intensity in the studied group. Moreover, the control group will wear headphones in silence while resting in the same conditions, this type of control (placebo) has not been described in the literature and won't allow an accurate sample calculation. Due to this, the first part of the study will be done as a pilot study for a better sample calculation.

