The SPSS for Mac, version 20, software was used for data analyses. For qualitative variables, frequency and percentages measurements will be used. For quantitative variables, central tendency measurements, variability and variance coefficients was used.

The primary endpoint for the study will be the effect of music in pain in dysmenorrhea. The secondary endpoints will be the impact in analgesic requirements, vital signs, and anxiety quantification. Comparative analysis will be performed to evaluate if a relationship between the level of pain and analgesic requirements, anxiety levels, and vital signs exist. Finally, multivariate analysis (MANCOVA) will be conducted to further test statistical significance for the pain relieving effect of music ($p < 0.01$).

4. Ethical considerations

This study is classified as minimum risk in accordance to the established regulations by the Resolution 008430 of 1993 from the Ministry of Health of Colombia (Scientific, technical, and administrative norms for the research in health).

All participants from the study will enroll and participate on their own desire and no person will be obligated to enroll, continue or complete the study participation. The study will not expose participants to drug interventions, surgical procedures or diagnostic procedures, physical therapy or other type of intervention that will add potential risks to physical integrity of participants. The study will be conducted in the Quinta de Mutis of the Universidad del Rosario, Bogota city. Therefore, no exposure to ambient risks will be related to this research. The sole intervention patients will receive is music through headphones. For conducting this research all recommendations from Helsinki declaration by the World Medical Associations will be considered.

5. Activity chronogram

ACTIVITY	MES															
	1	2	3	4	5	6	7	8	9	10	11	12	13	14	15	16
PROTOCOL DEVELOPMENT																
SEARCH FOR ADDITIONAL FUNDING IF REQUIRED AND IRB SUBMISSION																
DATA COLLECTION																
DATA ANALYSES																
PATIENT RECRUITMENT ACCORDING TO ELIGIBILITY CRITERIA																

¹ [not in the original protocol] – Note: before doing the first intervention it was deemed more appropriate to perform an interim analysis than a pilot study -.

INTERVENTION AND DATA COLLECTION FROM INCLUDED PATIENTS			
DATA ANALYSES			
DISCUSSION OF DATA ANALYSES			
COMPLETE RESULTS REPORT			
MANUSCRIPT PREPARATION			
SUBMISSION FOR PUBLICATION			

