5. Did you take any drug for pain relief during your last menses? YES NO

Drug name: _____

Used doses (Number of tablets): _____

E.g. Ibuprophen 4 tablets of 800 mg

6. Did you use any form of non-pharmacological strategy for pain relief during your last menses? YES NO

Specify: _____

For this part please read carefully instructions

Visual analog scale (VAS) consist of a 10 cm line. The line is marked with a 0 in one side and 10 in the other, and consider 0 as the least possible intensity and 10 as the greatest. For using the tool you have to put a mark that represents the perceived intensity that better answers the question.

7. Consider 0 (I have never felt pain during menses) and 10 (I always feel my worst kind of pain). Which is your usual pain associated to menses?

SUPPLEMENT 4. Questionnaire for the day of the intervention

STUDIED VARIABLES

The following document will be of exclusive use for the researchers during the day that the study is conducted. TIME: _____

Please answer the following questions.

1. With a single mark please answer. How much pain are you feeling right now? Consider 0 as "I'm not feeling any pain" y 10 "I'm feeling the worst pain of my life" (patient must answer by herself).

0  10

2. Please answer the following questions with: Never, Sometimes, Most of the time o Always.

Question	Never	Sometimes	Most of the time	Always
Have you felt nervous or anxious lately				
Have you felt fearful lately				
Have you been irritated or have you panicked easily				
Have you felt down				
Have you felt tremulous				
Have you felt headache, pain on your back, or pain on your neck				
Have you felt weak and fatigue easily				
Have you felt palpitations or elevated heart rate				
Have you felt dizzy lately				
Have you felt nausea or stomach disturbances lately				

3. Answer Yes or No. Would you take an analgesic drug or other would you do another analgesic strategy at this moment? If Yes, please specify:

4. At this moment how much time have you felt pain?

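### The 3-6 hour take-home form has no Yes/No for analgesic use, so on a returned form an empty table cannot separate none taken from not answered

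*Combined protocol and SAP*

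**What the plan says.** The Data collection section defines the later analgesic record as "AR2, used drugs or other analgesic therapies up to 6 hours after the intervention". The Procedure says of the form that carries it: "This questionnaire should be answered by the student 3-6 hours after the intervention". The form is then to be delivered to the investigators.

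Supplement 5 is that form. Under the lead-in "Complete the following tables" it has two items:

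- Item 1 (drug, time, quantity): "If you have taken any kind of analgesic drug please fill this table with the following information".
- Item 2 (strategy, time, duration): "If you have performed any form of non-pharmacological strategy for pain please fill this table with the following information".

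Neither item has a Yes/No or a box for none, and no instruction covers a student who used nothing. The definition of analgesic requirements during the day, under Variables and measurement tools, lists drug name, presentation, dose and time and adds no Yes/No. The same form has a TIME field, a pain VAS and ten anxiety items, introduced by "Please answer after 3-6 hours have passed from receiving the intervention".

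The trial's other forms ask differently. Supplement 2, item 5 reads "Did you take any drug for pain relief during your last menses? YES NO", and item 6 prints the same choice for non-drug strategies. Item 3 of Supplement 4, before and after the session, asks for an explicit Yes or No.

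Analgesic requirement is a secondary endpoint (Data analyses). Its specific objective names two times: after the intervention, and 3 to 6 hours later. Data analyses says only "For qualitative variables, frequency and percentages measurements will be used". It gives no scoring rule, no named test for this endpoint and no rule for missing items.

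**The concern.** AR2 is the only structured record of what a student actually took after the session. AR1, collected by the researcher at the end of the session, asks what she would like to take at that moment. The Procedure lets her start her usual analgesia only after those measurements.

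If an empty AR2 table can mean two things, no later coding rule recovers the difference. Reading every blank as no use turns some users into non-users. Reading every blank as missing discards every true non-user. The first is the more natural choice, and it lowers recorded use in whichever arm skips the table. At stake is the 3-6 hour comparison of analgesic use. The reading of the 3-6 hour pain score is also affected, since that score depends on what was taken.

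**Working it through.** **1. The plan's own figure.** The only sample-size figure is for the primary endpoint: n = 2 × (2.33 + 1.28)² × 2² / 1.5² = 2 × 13.0321 × 4 / 2.25 = 46.34, so 47 per group. It reproduces and does not depend on AR2. No figure is given for the analgesic endpoint.

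**2. What an empty table can mean.**

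| What is received | Reading |
|---|---|
| Form not returned | Missing, and recognisable: VAS, anxiety items and TIME are absent too |
| Returned, table filled | Use |
| Returned, table empty | Took nothing, or did not answer: not separable |

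The defect is confined to the last row.

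**3. Equal skipping, blanks read as no use.** From the documents: 47 per arm, and the one-sided 0.01 level, which is borrowed from the primary calculation because none is set for AR2. Assumed: true use 80% (silence) v 55% (music), and the fraction s of users who skip the table.

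Observed use = true use × (1 − s). Power = Φ(difference / SE − 2.326), with SE = √[(p₁(1 − p₁) + p₂(1 − p₂)) / 47].

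| s | Observed use | Difference | SE | Power |
|---|---|---|---|---|
| 0 | 80% v 55% | 25.0 points | 0.0931 | 0.64 |
| 10% | 72% v 49.5% | 22.5 points | 0.0980 | 0.49 |
| 20% | 64% v 44% | 20.0 points | 0.1007 | 0.37 |

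In women, s = 10% is 47 × 0.80 × 0.10 = 3.8 in the silence arm and 47 × 0.55 × 0.10 = 2.6 in the music arm.

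**4. A second set of assumptions.** The Background gives 91.3% drug use among students of the target population. Against an assumed 65% with music, and a two-sided 0.05 test with pooled variance under the null (also assumed), the difference is 26.3, 23.7 and 21.0 points at s = 0, 10% and 20%. Power is 88%, 72% and 56%. The direction does not depend on the inputs chosen in step 3.

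**5. Unequal skipping with no true difference.**

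- True use 75% in both arms, 5% (silence) v 20% (music) of users skip: 0.75 × 0.95 = 71.25% v 0.75 × 0.80 = 60%, a false gap of 11.25 points.
- True use 91.3%, 5% v 15% skip: 86.7% v 77.6%, a false gap of 9.1 points. A two-sided 0.05 test would favour music about 21% of the time.
- Equal skipping with equal use gives no false gap.

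**6. What a Yes/No would recover.** Suppose users who skip also leave the Yes/No unmarked, all non-users answer, and unmarked items are treated as missing. The 75% example with 5% v 20% skipping becomes 0.7125 / (0.7125 + 0.25) = 74.0% v 0.60 / (0.60 + 0.25) = 70.6%. The false gap falls from 11.25 to about 3.4 points. It shrinks but does not vanish.

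**The case against.** A reader might infer that the endpoint counts non-response as success. The documents do not support that. No section says that a blank is coded as no use, and the sentence on frequencies and percentages is generic. Because the variable is defined by drug, presentation, dose and time, an analysis by dose is equally open. Coding blanks as no use is a risk, not a stated rule.

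A reader might also infer that the whole analgesic endpoint is compromised, or that the form is biased towards music. Neither follows. AR1 has a Yes/No, and an unreturned form is visible as missing. Equal skipping shrinks a true difference, so it works against the music claim. A false benefit needs more skipping in the music arm, and no mechanism for that is documented. The note in the Procedure that the final speech disclosed neither the experimental group nor the pain outcome makes an expectation effect less likely.

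Further objections are fair. The form is delivered to the investigators, so an empty table could be queried then, and the general lead-in may prompt some students to write something. Skip rates and the true-use contrasts are assumed throughout. A Yes/No can itself be skipped.

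All of this limits size and direction. It does not remove the ambiguity: the plan describes no check on delivery, and the lead-in does not tell a non-user what to write.

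**Conclusion.** The point holds for one time point of one secondary endpoint. On a returned Supplement 5, an empty table cannot distinguish none taken from not answered, and the plan states no rule for blanks. The other analgesic-use questions avoid this with an explicit Yes/No.

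The size cannot be estimated from the documents. If blanks are read as no use and a tenth to a fifth of users skip in both arms, the illustration loses 2.5 to 5 points of a 25-point difference, and power falls from 0.64 to 0.49 or 0.37. These figures rest on assumed use, assumed skip rates and a borrowed significance level. A false difference is possible only if skipping differs by arm, for which there is no evidence. AR1, the primary endpoint and the sample size stand. Severity: minor improvement.

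**What to change.** - In Supplement 5, print a YES/NO question before each of the two tables, in the form that Supplement 2 already uses, and ask for the table only after YES.
- Score AR2 from the YES/NO. Treat an unmarked YES/NO with an empty table as missing.
- Check both items when the student hands the form to the investigators.
- Report the number missing by arm, with a sensitivity analysis that counts them all as no use and then all as use.

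If forms have already been collected in the present layout, the distinction cannot be restored. Report returned forms with empty tables by arm and run the same sensitivity analysis on them, bearing in mind that they include the true non-users.

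Cost: two tick-box lines, a short coding rule and a glance at delivery, with no extra participants or visits. Downside: a few AR2 values become missing instead of passing as no use, and some bias remains if skipping depends on use.
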